Specific Aims The *Central Hypothesis* is that telepalliative care has the potential to improve the quality of care delivered to pediatric palliative care patients in a rural state by connecting local care providers with palliative care interdisciplinary subspecialists at an academic health center to facilitate improved symptom burden which translates into enhanced quality of life for the pediatric patient and family members, increased confidence and comfort of local providers, and ultimately the creation of a unified and cross-setting shared care model.

Aim 1. To investigate the symptom burden for pediatric patients and the quality of life impact for pediatric patients and their families through an interdisciplinary pediatric telepalliative consultation service partnered with local hospice providers with an interface at a minimum of every 15 day intervals.

Aim 2. To evaluate the self-efficacy, knowledge, and self-perceived adequacy of local hospice providers in caring for pediatric patients before and after interdisciplinary pediatric telepalliative consultation service partnership with these local hospice providers.

Aim 3. To explore the acceptability of teleconferencing services as a form of pediatric palliative care mentorship for local hospice teams caring for children and adolescents.

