Description – This mixed-methods pilot feasibility study includes use of web-conferencing technology to connect a hospital-based interdisciplinary pediatric palliative care with statewide field-based adult hospice teams. The first collaborative meeting includes a comprehensive pediatric palliative care needs assessment completed with the patient, family, the pediatric palliative care team, and the local hospice team to include goals of care in symptom, relational, psychological, and spiritual domains as well as advance care planning content.⁴¹ The ongoing intervention with the hospice team includes either pediatric educational modules OR shared visits during interdisciplinary meetings (with the invitation to the patient and family for inclusion via tele-presence) at a minimum of 60-min every 15 calendar days.

Team-Approach – The study is specifically an interdisciplinary team empowerment design. The telepalliative team “interacts with the goal of transferring knowledge from one discipline to another; which allows members to inform each other’s work and compare findings”⁴² toward shared, collective outcomes.

Sample and inclusion criteria – The study population includes all patients ages birth to 18 years referred to the inpatient pediatric palliative care team at Children’s Hospital Omaha or the University of Nebraska Medical Center during hospitalization who are enrolling on home hospice services within the state of Nebraska at time of discharge from the hospital. Based on a chart review of three consecutive years (2013-2016), this situation includes an average of 30 pediatric patients per year. The mean age of this patient population based on three-year data is 7.4 years (range 3 days to 18 years); primary diagnosis included genetic (27%), oncology (23%), cardiac (18%), neurologic (18%), pulmonary (14%). Family distance from the hospital averaged 110 miles (range 7 to 320 miles). These children are noted to have a significant symptom burden to include pain, dyspnea, fatigue, nausea, and anxiety/depression.

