Selection methods and sample size – Pediatric patients and their families will be informed of the CALLINGS Protocol (Care Across Locations Longitudinally in Navigating Goals and Symptoms) at time of home hospice enrollment to foster consecutive sampling enrollment. The local nurse team hospice will receive telehealth interdisciplinary team meetings specific to patient need for up to 60 minutes every 15 days. The pilot study size of 10-20 patients per hospice is grounded in evidence-base for feasibility study sample population size rather than power scales.⁴³ Note that study duration would be for a maximum of six months per enrollee (due to hospice enrollment being a six-month commitment as standard).

- Pediatric patient-specific case discussions for enrolled pediatric patients at hospice staff interdisciplinary team meeting every 15 days for 60 min sessions via telehealth

[figure not shown]
home hospice enrollment to foster consecutive sampling enrollment. The local nurse team hospice will receive telehealth interdisciplinary team meetings specific to patient need for up to 60 minutes every 15 days. The pilot study size of 10-20 patients per hospice is grounded in evidence-base for feasibility study sample population size rather than power scales.⁴³ Note that study duration would be for a maximum of six months per enrollee (due to hospice enrollment being a six-month commitment as standard).

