- **Consent/Enrollment** - Consent and enrollment procedures will follow strict Institutional Review Board expectations and ethical standard.
- **Stakeholder Survey** – Local hospice team will be asked about their perceived self-efficacy (comfort), knowledge, and perceived adequacy in caring for pediatric children in using quantified Pediatric Palliative Care Questionnaire scale pre- and post-child enrollment.

- *Symptom Burden and Quality of Life* – Child, guardian, and hospice team nurse will complete Pediatric PROMIS-37™ every 15 days to assess for symptom burden and translated quality of life.
- *Interdisciplinary (IDT) Telepalliative Care Meetings* –Technology Acceptance Model survey will occur every 15 days (in the pediatric palliative educational arm and in the patient-specific case discussion arm) as an automatic screen on the closing telepalliative screen to evaluate acceptability of technology interface. The reason for this frequency is that Medicaid requires that hospice interdisciplinary team interactions occur at a minimum of every 15 days.
- *Team Debriefing* – At enrollment and at the conclusion of the study period (six months per enrollee with total project duration 2 years) or within 3 days following a child’s natural end of life; the local hospice team members will be invited to engage in a qualitative interview with two thematic topics: 1. Please describe your experience caring for a pediatric patient and 2. Please describe your experience with telepalliative use. This interview will be recorded and coded for content using Atlas.ti software.

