Data Plan – Descriptive statistics will be computed for each outcome variable at each time point. Repeated measures ANOVA and trend plots will be used to explore quantified symptom burden and quality of life trends over time. The association between individual and multiple symptoms will be explored via linear and multiple linear regression. Bland-Altman plots will be used to assess concordance between symptom and quality of life reporting. Crude (unadjusted) associations between demographics (such as family economics, diagnosis, level of technology, delay to initial palliative care) and symptoms / quality of life will be explored via ANOVA or linear regression, as appropriate. A similar analysis will be used to explore the association between how hospice team self-perceived confidence and knowledge of pediatric palliative care and child symptom and quality of life. In the event the assumptions of the parametric tests identified above are violated, the appropriate non-parametric test will be used. When a non-parametric test is used, the median and interquartile range for continuous outcomes will be reported. A significance level of 0.05 will be used to judge statistical significance. In addition to monitoring for statistical significance, the study team will follow minimally clinically important

difference (MCID) for symptom burden or quality of life values over time.⁵⁸ MCID has been defined as “the smallest difference in a score of a domain of interest that patients perceive to be beneficial and that would mandate, in the absence of troublesome side effects and excessive costs, a change in the patient's management.”⁵⁹ Content of the two qualitative interview questions will be analyzed thematically using a qualitative coding methodology in Atlas.ti ([name] has completed graduate level qualitative coursework >9 credit hours and published >4 qualitative method manuscripts).⁶⁰

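### Aim 1 asks for the telepalliative service's impact, but the Data Plan's within-child time trends cannot separate the service from hospital discharge, hospice start and dying

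*Combined protocol and SAP*

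**What the plan says.** Aim 1 (Specific Aims) is to investigate symptom burden and "the quality of life impact for pediatric patients and their families through an interdisciplinary pediatric telepalliative consultation service".

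The Data Plan answers this over time in one way: "Repeated measures ANOVA and trend plots will be used to explore quantified symptom burden and quality of life trends over time". It adds that "A significance level of 0.05 will be used to judge statistical significance", and that "the study team will follow minimally clinically important" difference (MCID) values over time. No MCID value is given, and the definition it cites is framed as benefit to the patient.

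On the start of follow-up, Sample and inclusion criteria takes children "who are enrolling on home hospice services within the state of Nebraska at time of discharge from the hospital". Selection methods and sample size has families informed "at time of home hospice enrollment to foster consecutive sampling enrollment". The forms are due every 15 days, but the date of the first form and of the first telepalliative meeting is not stated. No assessment before the service is described.

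On the end of follow-up, participation is capped at six months. Team Debriefing provides for an interview at the end of the study period or "within 3 days following a child’s natural end of life", so deaths during follow-up are expected.

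The study has two arms, pediatric education and patient-specific case discussion (Description; Step-by-step outline). The Project Abstract intends to learn which helps more, including for patient symptoms and family quality of life. The Data Plan names no arm or arm-by-time term.

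**The concern.** Discharge, hospice entry and the start of telepalliative contact fall at nearly the same moment, and every child gets some form of the intervention from then on. Early change in a score can come from recovery after the hospital episode, from hospice care itself, or from the service. Late change can come from dying or from the service. The only clock is time since enrolment, so the time term carries the sum of these and nothing in the analysis divides it.

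More children, complete forms or a better repeated-measures model would not help, because the missing element is a contrast. A service that does nothing could appear to help in the first weeks, and a useful one could be hidden by terminal decline. If the trend, its p-value or an MCID count were then offered as the answer to Aim 1, that answer could simply be the natural course.

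**Working it through.** The plan has no figure to reproduce. It states no effect size, SD, survival or score values, and the sample size is expressly not based on power. The following shows what the trend can do when the service does nothing.

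**Assumptions (none from the documents)**
- Survival from enrolment is exponential, with median m = 45, 90 or 150 days and rate λ = ln 2 / m.
- Lower scores are better.
- Discharge recovery, if any, is 3 points with a 10-day time constant.
- Terminal worsening, if any, is linear over the last 45 days of life, to 5 or 10 points.
- The day-30 change is taken in children alive at day 30.

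**No service effect, recovery only**
- First form at day 0: -3 × (1 - e^(-30/10)) = -3 × 0.950 = -2.85.
- First form at day 15: -3 × (e^(-1.5) - e^(-3)) = -3 × (0.223 - 0.050) = -0.52.

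**No service effect, terminal worsening only**

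For a child alive at day 30, remaining life is again exponential with rate λ. Let g(a) = (a/45) × [1 - (1 - e^(-λa))/(λa)]. The expected fraction of worsening present is g(45) at day 30, and was g(15) at day 0 in the same children. The expected change is the maximum worsening × [g(45) - g(15)].

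| Median survival | g(45) | g(15) | Change, 5 points | Change, 10 points |
|---|---|---|---|---|
| 45 days | 0.279 | 0.036 | +1.2 | +2.4 |
| 90 days | 0.155 | 0.019 | +0.7 | +1.4 |
| 150 days | 0.097 | 0.011 | +0.4 | +0.9 |

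With a first form at day 15, g(30) replaces g(15). The largest figure falls from +2.4 to 10 × (0.279 - 0.133) = +1.5.

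**True benefit of 3 points (20-day time constant), no recovery**

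The service alone gives -3 × (1 - e^(-30/20)) = -2.33 at day 30. Adding the table's columns gives:
- 5 points of worsening: -1.1, -1.6 and -1.9 for medians 45, 90 and 150.
- 10 points of worsening: +0.1, -1.0 and -1.5.

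The sign is right in five of six cells, but the benefit is understated in all six.

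**How often the planned test would be significant**

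One-group repeated measures ANOVA was simulated with zero service effect (4,000 runs, within-child correlation 0.5, complete follow-up, linear drift totalling 0.5 outcome SD). The two visit counts are 5, and the 13 that six months allow (180/15 = 12, plus baseline).

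| Children | 5 visits | 13 visits |
|---|---|---|
| 10 | 24% | 29% |
| 20 | 47% | 60% |

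With no drift, rejection is about 5%. If a 0.5 SD benefit is exactly offset by a 0.5 SD decline, the net trend is zero and the test again rejects about 5% of the time. On the same simulated data split into two equal, comparable arms, a between-arm test of slopes rejects in 4.5% to 5.2% of runs whatever the drift.

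**The case against.** The strongest reply is that the plan does not claim what is being criticised. Table 1 calls this an exploratory pilot feasibility study, the Data Plan uses trends to explore, the hypotheses speak of potential, and Commitment to Share Findings treats improvement as an open question. That stands. A reader might infer that the plan will announce from these trends that the model improves symptoms, or will count MCID movement as benefit. No text says so. What remains is Aim 1's wording of impact through the service, a 0.05 test on the trend, and nothing restricting how the result may be reported.

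A second reply is that the study has a concurrent comparison. It does, and the arms share the same clock, so a between-arm difference in change would remove common recovery and decline if allocation is comparable. A figure beside the sample-size text is not shown, so allocation cannot be judged here. But the Data Plan specifies no such analysis, and the contrast would estimate mentorship versus education, not the service versus hospice alone. The planned association of hospice-team confidence and knowledge with child outcomes does not isolate a service effect either.

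Third, the numbers are assumed. No document shows discharge recovery in these children or dates the first form, and a day-15 start removes most of the early artefact. A reader might also want the change from enrolment to the last form, where terminal decline would weigh most. The Data Plan never proposes that summary, so it is no evidence against the plan.

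**Conclusion.** The point holds as a limit on interpretation. Followed as written, the Data Plan gives a time trend that cannot be attributed to the service in either direction. That conclusion rests on the entry criteria, the absence of scores before the service, and the end of follow-up at six months or death; it needs none of the assumed figures.

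The size is unknown. Under the stated assumptions and a first form at enrolment, a null service could show an expected day-30 change from about -2.9 to about +2.4 points. The recovery end falls to about -0.5 with a first form at day 15. It would be wrong to conclude that the study lacks any comparison, or that it already claims efficacy. In an exploratory pilot this is an inexpensive improvement that should be made before the trends are reported.

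**What to change.** In the Data Plan:

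1. State that within-child time trends, their p-values and MCID movements describe the course under hospice plus telepalliative care and will not be reported as an effect of the service. Reword Aim 1 to 'describe' for these trends.
2. Classify MCID movement as improved, stable or worsened.
3. For children who die on study, also plot scores by days before death, using the death date already needed for the 3-day debriefing. Add separate early and last-30-day summaries only if numbers allow. Non-overlapping first-30 and last-30-day windows need a death between day 60 and day 180, with probability 2^(-60/m) - 2^(-180/m) = 33%, 38% and 32% for medians 45, 90 and 150. That is roughly 3 to 8 of 10 to 20 children.
4. Base any comparative statement on symptoms or quality of life on the between-arm difference in change, labelled exploratory and as mentorship versus education.

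The cost is some wording, one extra set of plots and one between-arm summary, all from data already collected. The study gives up an efficacy-type statement from the time trend.

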CALLiNGS Protocol: Care Across Locations Longitudinally of Goals and Symptoms

NCT : pending

June 23, 2018

Junior Faculty Career Development Award

**CALLiNGS Protocol: Care Across Locations Longitudinally in Navigation of Goals and Symptoms
Interdisciplinary Pediatric Telepalliative Consultations for Hospice Teams**

Project Abstract

Despite 35+ pediatric hospice discharges to rural providers each year in Nebraska; primary care providers, hospice directors, and hospice nurses in Nebraska report they feel unprepared to manage pediatric hospice patients. In this pilot intervention study guided by the Theory of Unpleasant Symptoms, web conferencing services will connect an inpatient pediatric palliative care team with adult outpatient hospice providers to support local providers in assessing pediatric-specific care needs and implementing developmentally-appropriate pediatric treatment plans for 10-20 medically-complex children. The objective of this CALLiNGS (Care Across Locations Longitudinally in Navigation of Goals and Symptoms) mixed-methods study is to test feasibility, acceptability, and quality of life outcomes from using web-conferencing technology to connect a hospital-based interdisciplinary pediatric palliative care with statewide field-based hospice teams during interdisciplinary meetings at a minimum of every 15 calendar days. The reason for selection of every 15 days is because Medicaid requires that interdisciplinary hospice teams meet at a minimum of every 15 days to review patient symptom burden, medications, and plan of care. The study team hypothesizes that telepalliative care for children has the potential to improve the quality of care delivered to pediatric palliative care patients in a rural state by facilitating the confidence and comfort of local providers, enhancing goals of care conversations, improving symptom management for patients and therefore quality of life for family members, and creating a unified and cross-setting shared care model. The study intends to determine whether direct patient-specific pediatric mentorship or general pediatric palliative education is more helpful for hospice staff, for patient symptoms, and for family quality of life. If feasible this model could transform the pediatric palliative care delivery in the state of Nebraska with expanded opportunity for application in settings with similar subspecialty provider shortages.

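### The only test planned for change in the 15-day scores ignores visit order and direction; add a signed mean slope with a confidence interval beside a sphericity-corrected ANOVA

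*Combined protocol and SAP*

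**What the plan says.** The Data Plan (Research Design and Methods) gives one inferential method for change in the longitudinal scores: "Repeated measures ANOVA and trend plots will be used to explore quantified symptom burden and quality of life trends over time". The threshold is fixed: "A significance level of 0.05 will be used to judge statistical significance". If assumptions fail, "the assumptions of the parametric tests identified above are violated, the appropriate non-parametric test will be used"; that test is not named. No slope, linear contrast, random-slope model or sphericity correction appears. Descriptive statistics at each time point and tracking of the minimally important difference are also planned.

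The hypothesis has a direction. The Central Hypothesis under Specific Aims expects the service "to facilitate improved symptom burden which translates into enhanced quality of life", and the Project Abstract speaks of "improving symptom management for patients and therefore quality of life for family members".

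Scores are due every 15 days (Table 1; step-by-step outline), and "study duration would be for a maximum of six months per enrollee". The Abstract plans "developmentally-appropriate pediatric treatment plans for 10-20 medically-complex children"; the sample-size section gives the same range per hospice and says that it does not rest on power.

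**The concern.** The occasion effect in repeated measures ANOVA is an unordered, directionless test. Shuffling the visit labels leaves F unchanged, and worsening rejects as readily as improvement. The p-value therefore does not answer whether scores improve, and no planned estimate of average change with an interval does so either.

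The F-test also relies on sphericity. Scores taken 15 days apart on the same child are likely to be serially correlated, and some children may improve while others decline. Either feature breaks sphericity and raises the rejection rate above 0.05 unless a correction is applied.

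At stake is the reading of Aim 1. Taken alone, a significant F does not show improvement. A non-significant F from 10-20 children says little about a steady change.

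**Working it through.** **Inputs from the documents.** 10-20 children (Abstract); α = 0.05 (Data Plan); one score per 15 days for up to six months, 180/15 = 12 intervals, so 12 occasions (13 if enrolment is scored as well). The plan gives no power, effect size, SD or correlation, so there is no figure of its own to reproduce.

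**Assumptions.** Complete data. Score = child level (variance 0.5) + visit-to-visit process (variance 0.4, lag-1 correlation ρ) + measurement error (variance 0.1, from the reliabilities of 0.88 and 0.90 under Study Variables and Measures) + (mean slope + child's own slope deviation) × time, with time running from 0 to 1 over six months. The total SD at enrolment is 1. Divergence is the SD of the children's slopes. The slope test is a two-sided t test on per-child least-squares slopes, the balanced-data counterpart of a random-slope mixed model; the mixed model itself was not fitted.

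**1. Degrees of freedom, 12 occasions.** Omnibus F: 11 and 11(n−1), that is 11 and 99 (n=10) or 11 and 209 (n=20). Slope test: 1 and n−1, that is 1 and 9 or 1 and 19.

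**2. Power for a steady common change of 0.5 SD, ρ=0, no divergence.** Both tests share the noncentrality λ = n·δ²·Σ(t−t̄)²/σ². Here Σ(t−t̄)² = k(k+1)/[12(k−1)] = (12×13)/(12×11) = 1.182 and σ² = 0.4+0.1 = 0.5.
- n=10: λ = 10×0.25×1.182/0.5 = 5.91. Power: F 27.6%, slope 58.2%.
- n=20: λ = 20×0.25×1.182/0.5 = 11.82. Power: F 58.6%, slope 90.3%.

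**3. The gap against a corrected ANOVA.** Simulated, 0.5-SD mean change, ρ=0.5, 12 occasions:

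| Slope SD | n=10: corrected F / slope | n=20: corrected F / slope |
|---|---|---|
| 0 | 15-16% / 36-37% | 45-46% / 67% |
| 1 | 13% / 18% | 31% / 36% |
| 2 | 9.0% / 9.6% | 16.5% / 16.5% |

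Series length, from a separate set of runs (within-child SD 1, ρ=0.5, common change of 1, no divergence), corrected F against slope:
- n=10: 34.0% v 58.6% with 13 occasions (24.6 points); 39.1% v 52.3% with 7 (13.2 points).
- n=20: 77.1% v 90.5% with 13 (13.4 points); 76.7% v 85.0% with 7 (8.3 points).

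**4. Rejection when the average trend is zero (nominal 5%).**

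| Setting | Uncorrected F | Friedman | Slope |
|---|---|---|---|
| 4 occasions, slope SD 1, ρ=0.5 | about 7% | about 5% | about 5% |
| 12 occasions, slope SD up to 0.5, ρ 0.5-0.7 | 7-9% | 5-7% | about 5% |
| 12 occasions, slope SD 1-2, ρ 0.5-0.8 | 9-16% | 7-11% | 4.5-5.4% |

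In the separate runs the Greenhouse-Geisser-corrected F stayed at or below about 5.6% throughout.

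**5. Where the slope does worse.** Change of 1, ρ=0.5, slope SD 0.5, 12 occasions:
- Gain over the first quarter, then plateau: corrected F 66% v slope 51-52% (n=10); 98% v 86% (n=20).
- Rise then fall: corrected F 66% v slope 4-5% (n=10); 99% v 5% (n=20).

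**The case against.** The study is an exploratory pilot, titled as such in Table 1 and not sized on power. Its hypothesis claims only potential benefit and specifies no straight-line course. When the shape of change is unknown an omnibus test is defensible, and step 5 shows that it can be the better one. Occasion-by-occasion summaries, trend plots and tracking of the minimally important difference would show direction beside the p-value. This stands as a reason to keep the ANOVA. It does not remove the point: the plan still judges significance at 0.05, and those displays neither estimate average change with an interval nor alter what the p-value tests.

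The plan also does not exclude a sphericity correction, and it does not name Friedman's test. Both are correct. The excess rejections belong to an uncorrected F, and the Friedman figures apply only if that test, the usual rank counterpart, is the one chosen.

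Finally, the power loss and the excess rejections do not peak together. The gap of about 30 points needs no serial correlation and no divergence; the largest inflation needs strong divergence over 12 complete occasions. In home hospice, with forms completed as the child is able, shorter series are likely, and both effects are then smaller.

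**Conclusion.** The concern holds in a limited form. The one named test of change does not estimate the hypothesised improvement, and no sphericity correction is specified. That much follows from the text and needs no simulation.

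The size depends on assumptions, because the documents give neither serial correlation nor divergence. At ρ=0 the loss against a slope test is 58.2−27.6 = 30.6 points (n=10) or 90.3−58.6 = 31.7 points (n=20). Against a corrected ANOVA the gap shrinks with shorter series and is nil at slope SD 2. Excess rejection of the uncorrected F runs from about 7% to 16%. All figures assume complete data; deaths and missed forms were not modelled. If the 10-20 applies per hospice and several hospices are pooled, power rises for both tests.

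A reader might infer that the ANOVA should be replaced, that false positives will generally run at two to three times 0.05, or that the plan commits to Friedman's test. The documents support none of these: they leave the shape of change, the correction and the fallback open, and the omnibus test is the better detector of some plausible courses.

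**What to change.** In the Data Plan, keep repeated measures ANOVA and trend plots, state that the Greenhouse-Geisser correction will be applied, and add:

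> Average change in each score will be estimated as the mean slope per 30 days since enrolment, from a mixed model with linear time and a child-level random intercept and slope with small-sample degrees of freedom (or, if it does not converge or its assumptions fail, from per-child fitted slopes with a signed-rank test), reported with sign and 95% CI. Claims of improvement or worsening will rest on this estimate; the corrected ANOVA will be used to detect non-linear change.

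State also that Friedman's test will not be the sole fallback for the 15-day series. The slope test must use between-child variation in slope: with 13 occasions, 10 children and a slope SD of twice the within-child SD, a pooled-error linear contrast rejects a true zero trend 34% of the time and Page's trend test 28%.

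The cost is wording and one extra analysis per score; forms, children and schedule are unchanged. Because a linear slope is insensitive to early-plateau and rise-then-fall courses, the corrected omnibus test should stay beside it as a test and not be reduced to description.

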This research proposal is innovative not only for the application of advanced technologies but also for the model of collaboration across care ages (continuum of care) and empowerment of medical homes.²³ The research proposal is innovative in relying not only on proxy report in the form of provider and parent perspective, but, in also eliciting direct child voice (an oft-silenced voice in the field)²⁴ for impact metrics. The research is innovative in inclusiveness by welcoming grandparent and sibling perspectives in family impact scales, a seemingly ignored and yet impacted population.^{25,26,27} The research is innovative in recognizing opportunity for collaborative energy through consultation-based care for children (addresses silo-ed subspecialty care as a critical barrier to progress in caring well for children with palliative care needs). The research is grounded in the Theory of Unpleasant Symptoms (TOUS),^{28,29,30,31} which theorizes that symptom intensity is illness and situation specific with variables that influence it but cannot be changed (such as the ill child's diagnosis, age, and gender) and that mood (depression, anxiety) can influence synergistic symptoms (fatigue, pain, nausea) which culminate in an influence on overall family function. Thus, the research is progressive in placing biological impact within context of whole-family psychosocial quality of life experience.

Conceptual Framework –

Theory - The theory which frames this study is the Theory of Unpleasant Symptoms (TOUS). This theory was developed to explore the understanding of relationships among multiple symptoms and how changes in symptoms translate into lived experience.³² TOUS is thus recognized as a “middle-range” predictive theory.^{33,34} TOUS has been used to develop preventive interventions to adjust influencing factors for improved symptom profile and thus improved quality of life with measured outcomes for adults.^{35,36,37} Application of this theory for a pediatric population is highly-relevant and novel.

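### The planned symptom-association regressions blend between-child and within-child association, and if all visits are pooled they also treat repeated scores as independent

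*Combined protocol and SAP*

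**What the plan says.** The Data Plan gives this analysis one sentence: "The association between individual and multiple symptoms will be explored via linear and multiple linear regression". It does not say whether all visits, one visit or child means enter the regression. It names no child effect, centring, mixed model or clustered standard error for this purpose. Repeated measures ANOVA is assigned to trends over time only. The fallback for violated assumptions is an unnamed non-parametric test, which does not separate the two levels either. A 0.05 significance level applies throughout.

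The data are repeated. Under the step-by-step outline (Symptom Burden and Quality of Life), the child, "guardian, and hospice team nurse will complete Pediatric PROMIS-37™ every 15 days". Under Selection methods and sample size, "study duration would be for a maximum of six months per enrollee".

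The Conceptual Framework supplies the question. On the Theory of Unpleasant Symptoms it says "This theory was developed to explore the understanding of relationships among multiple symptoms and how changes in symptoms translate into lived experience", and under Concepts it describes symptoms as setting one another off.

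**The concern.** There are two different questions. One is whether children who have more of one symptom also tend to have more of another (between children). The other is whether, when one symptom changes in a given child, another changes with it (within a child). The theory's language about changes in symptoms, and about symptoms amplifying each other, points to the second. A single ordinary regression slope does not isolate it.

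The source population is mixed. It covers five diagnosis groups, and "The mean age of this patient population based on three-year data is 7.4 years (range 3 days to 18 years". Stable differences between children are therefore plausible and can dominate the slope. At stake is whether a reported association can be read as symptoms moving together in a child. The repeated forms already planned could answer that, but the analysis as written does not use them for it.

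**Working it through.** **Inputs from the plan.** Forms come every 15 days for at most six months: about 182 / 15 ≈ 12 follow-up forms, or 13 with baseline, per reporter. There are 10-20 children; the Project Abstract gives this as a total and Selection methods as a number per hospice. Alpha is 0.05, taken as two-sided because the plan does not say. The plan gives no intraclass correlation (ICC), symptom correlation or standard deviation, and sizes the study without a power calculation, so there is no figure to reproduce.

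**Assumptions.** Both symptoms have the same variance and the same ICC, 0.5 unless stated. Stay on study is exponential with a median of 60 days, giving 1-13 forms and about 5.6 per child. r_b and r_w are the between-child and within-child correlations.

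**1. Slope from all records or one visit.** Its large-sample value is

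slope = ICC × r_b + (1 − ICC) × r_w

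| r_b | r_w | Formula | Simulated pooled slope | Reading |
|---|---|---|---|---|
| 0.6 | 0 | 0.5×0.6 + 0.5×0 = 0.30 | 0.28-0.29 (6 or 12 forms per child) | positive with no within-child link |
| 0 | 0.4 | 0.5×0 + 0.5×0.4 = 0.20 | 0.21-0.23 | diluted |
| 0.6 | 0.4 | 0.5×0.6 + 0.5×0.4 = 0.50 | 0.49 | overstated |
| −0.4 | 0.4 | 0.5×(−0.4) + 0.5×0.4 = 0 | 0.03-0.05 | cancelled |

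**2. Slope from child means.** With m forms per child,

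slope = [ICC × r_b + (1 − ICC) × r_w / m] / [ICC + (1 − ICC) / m]

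At ICC 0.5 and m = 6 the weights are 0.5 / (0.5 + 0.083) = 0.857 on r_b and 0.143 on r_w, so the slope is mainly between-child. With r_b = 0 and r_w = 0.4 it is 0.143 × 0.4 = 0.057. In simulation, child means detected that within-child link in only 5-7% of studies.

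**3. Pooling as independent rows.** With r_b = r_w = 0, pooled regression was significant in about 20-24% of simulated studies of 10-20 children. With ICC from 0.3 to 0.7 and 6 or 12 forms per child, the range was 10-46%. The child-centred slope stayed at 4-6%.

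**4. Share of studies with p < 0.05, for 10 / 20 children.**

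| r_b, r_w | Pooled | Pooled, child-clustered errors | Within-child slope |
|---|---|---|---|
| 0.6, 0 | 50% / 75% | 35% / 55% | 4-5% |
| 0, 0.4 | 44% / 56% | not run | 79% / 98% |
| 0.6, 0.4 | 91% / 100% | not run | 79% / 96% |

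Clustered errors remove part of the excess in the first row, but they leave the blended slope unchanged. In that row ICC matters: at 0.2 the pooled share falls to 13% / 26%.

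**5. Check on the remedy.** The 4-5% assumes that visit deviations are independent over time. With lag-1 autocorrelation of 0.5, the child-centred slope rejects falsely in about 10% of studies. With an assumed shared terminal rise of 1-1.5 SD in both symptoms, it rejects in 10-44%. The replacement model therefore needs a guard against serial correlation and a stated limitation.

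**The case against.** The strongest reply is that this is a modest exploration and is worded modestly. That largely stands:

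- **Not a main analysis.** None of Aims 1-3 concerns links between symptoms. A reader might infer that this regression carries the study's theory, but the Conceptual Framework names symptom burden, translating into quality of life, as the outcome of interest.
- **No claim of direction.** A reader might infer that the plan would report symptoms as driving each other. The Data Plan speaks only of association. The theory section invites the stronger reading, but the analysis text does not make it.
- **A between-child reading is legitimate.** Background and Significance speaks of co-occurring symptoms and clustering, and Innovation lists fixed influences such as diagnosis, age and gender. A between-child association describes these properly.
- **The 50% / 75% is not a false-positive rate.** That setting contains a real between-child link, so declaring an association is correct. Only a within-child interpretation would be wrong. Part of the figure is also due to treating repeated scores as independent.
- **Within-child links are not generally missed.** That happens when the between-child link is weak or opposite, or when one visit or child means are used. When both links are positive, pooled regression finds the association and overstates it.
- **The sentence is ambiguous.** It names no outcome and could mean single and combined symptoms against quality of life. The level problem would remain, but statements about symptom clusters would not apply.

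The reply does not remove the central point. Nothing in the plan separates the two levels or fixes the unit of analysis, a 0.05 threshold will be applied, and publication is planned.

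**Conclusion.** The point holds as a flaw in how a secondary, exploratory result could be interpreted. The slope as planned cannot show whether symptoms move together within a child. Depending on the between-child link, it can be positive with no within-child link, diluted (about 0.22 against 0.40), overstated (about 0.49 against 0.40) or close to zero. If visits are pooled as independent rows, the test is also anti-conservative (about 20-24% with no link at either level).

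The blending follows from the algebra. Its size does not: it rests on assumed ICC, correlations, equal variances and length of stay. Whether 10-20 is a total or a number per hospice affects precision, not the blending. The documents do not support the wider inference that the study's main conclusions are at risk.

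**What to change.** Replace the Data Plan sentence with:

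> For each reporter with enough repeated forms, associations between symptoms will be estimated with a linear mixed model with a random intercept per child, days since enrolment, and either a serial (AR(1) or continuous-time) residual correlation or small-sample cluster-robust standard errors. Each symptom predictor will be split into the child's mean and the visit's deviation from it. The within-child and between-child slopes will be reported separately, both as associations and not as evidence of direction.

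The sponsor should set in advance how many forms count as enough. This matters most for self-report, which Table 1 makes conditional on the child's ability.

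The cost is a wording change and slightly more analysis, with no new data or visits. There are two downsides to state. A child with one form adds nothing to the within-child slope. A shared decline near the end of life can still produce a within-child association, and this should be reported as a limitation.
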